3.3.7. Days of Ventilation/ECMO

Ventilator / ECMO days will be defined as the number of days where the clinical status score is equal to 7. After discharge, the CRF question regarding days of ventilation will be used. The total number of days will be the sum of all reported days, regardless of whether the days occur consecutively or in disjoint intervals. See Section 6.5 for the plan for handling subjects who do not have data through Day 29 or die prior to Day 29.

3.3.8. Days of Oxygen

Oxygen days will be defined as the number of days where the clinical status score is equal to 5, 6, or 7. After discharge, the CRF question regarding days of oxygenation will be used. The total number of days will be the sum of all reported days, regardless of whether the days occur consecutively or in disjoint intervals. See Section 6.5 for the plan for handling subjects who do not have data through Day 29 or die prior to Day 29.

3.3.9. Days of Hospitalization

Duration (in days) of hospitalization will be defined as the number of days from randomization to discharge. For the secondary outcome, duration of the initial hospitalization will be used only. See Section 6.5 for the plan for handling subjects who do not have data through Day 29 or die prior to Day 29.

3.3.10. Time to Death

For analysis of time to death, the time to death will be defined as the elapsed time (in days) from randomization (or treatment administration for the safety analysis) to death. Any subjects that are lost to follow-up or terminated early prior to death will be censored at the day of their last observed assessment or last captured event (e.g. the end date of an adverse event). If it is learned that a subject who terminated early had subsequently died prior to Day 29, then the subject will be classified as dead. Subjects who complete follow-up will be censored at the earliest of their Day 29 visit and (actual Day 29). Deaths that occur after Day 29 will be censored at Day 29.

Similar censoring methods will be used for the 14-day mortality analyses in that deaths that occur after Day 15 will be censored at Day 15 and subjects who are confirmed alive through Day 15 will be censored at Day 15. Subjects whose last observed assessment or last capture event (e.g. the end date of an adverse event) is prior to Day 15 will be censored at that last observed assessment/event.

Sensitivity analyses will be performed where subjects who were unblinded and retreated with remdesivir will be censored at the time of remdesivir treatment initiation. A similar process will be used for the unblinding sensitivity analysis.

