8.2.3. Days of Oxygenation

Duration of oxygenation days will be summarized in a table using medians and quartiles by treatment arm (Table 41). This will only include subjects in category 5, 6, or 7 at enrollment. Analyses will be performed in the ITT population, Treated population, and a subset of the

Treated population of treated subjects only as subjects who are not treated are terminated from the study immediately and are included in the ITT/Treated analyses with a count of 1 day. Bee swarm plots of oxygen days by treatment arm will be generated, where subject whose days are imputed to the maximum of 28 days due to death are grouped separately from subjects who do not die (Figure 17).

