9.4. Deaths, Serious Adverse Events and other Significant Adverse Events

A listing of death and other serious adverse events will be presented, including Subject ID, treatment group, Adverse Event Description, Associated Dose Number, Number of Days Post Dose (Duration), Number of Days Post Dose the Event Became Serious, Reason Reported as an SAE, Severity, Relationship to Treatment, Alternate Etiology if not Related, Action Taken with

Study Treatment, Subject Discontinuation, Outcome, MedDRA SOC, and MedDRA PT (Listing 12 and Listing 13).

The number of subjects who die by Day 15 and Day 29 will be presented by treatment arm. The 14- and 28-day crude mortality rate, which will use the number of subjects in the treatment group and analysis population as the denominator, will be presented (Table 59). The analysis will be repeated censoring placebo subjects who were retreated with remdesivir at the time of retreatment.

Mortality through Day 15 and 29 will also be analyzed as a time to event endpoint (see Section 3.3). A table will present median time to event along with 95% confidence intervals overall for each treatment arm along with the hazard ratio estimate and log rank p-values (Table 61). Differences in time-to-event endpoints by treatment will be summarized with Kaplan-Meier curves (Figure 23). Analyses of mortality will be performed in the ITT and the Treated analysis populations and will be performed on both the early and the full analysis sets.

The ITT tabular summaries will be repeated censoring placebo subjects who were retreated with remdesivir at the time of retreatment. Similarly, the summaries will be repeated censoring subjects who were unblinded at the time of unblinding.

Rates of Grade 3 and 4 AE occurrence will be compared between treatment arms using Barnard's exact test and presented (Table 63). Rates of SAE occurrence will also be compared between treatment arms using Barnard's exact test and presented. Further, the composite endpoint of the occurrence of death, SAE, or Grade 3 or 4 AE described in Section 3.3 will be analyzed as a time to event outcome. A table will present median time to event along with 95% confidence intervals overall for each treatment arm along with the hazard ratio estimate and log rank p-values (Table 64). Differences in time-to-event endpoints by treatment will be summarized with Kaplan-Meier curves (Figure 24).

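### The Day 29 time-to-death rule uses information learned after early termination only when it is a death, so follow-up depends on outcome and the mortality curve and hazard ratio can be biased

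*SAP*

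**What the plan says.** SAP 3.3.10 defines time to death. Subjects who are lost to follow-up or "terminated early prior to death will be censored at the day of their last observed assessment or last captured event". One exception follows: "If it is learned that a subject who terminated early had subsequently died prior to Day 29, then the subject will be classified as dead". It names early terminators only, not subjects lost to follow-up. The horizon is Day 29: "Deaths that occur after Day 29 will be censored at Day 29".

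For the 14-day analysis the same section adds that "subjects who are confirmed alive through Day 15 will be censored at Day 15". The next sentence censors anyone whose last assessment or captured event falls before Day 15 at that earlier point. The Day 29 analysis has no counterpart to the first of these two sentences.

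SAP 9.4 uses the variable as follows: "Mortality through Day 15 and 29 will also be analyzed as a time to event endpoint". It yields a hazard ratio, a log-rank p-value and Kaplan-Meier curves, in the ITT and Treated populations and in both the early and full analysis sets. SAP 9.4 also gives crude 14- and 28-day mortality, "which will use the number of subjects in the treatment group and analysis population as the denominator".

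One source of early termination is documented. SAP 8.2.3 notes that "subjects who are not treated are terminated from the study immediately", and these subjects remain in the ITT population.

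**The concern.** Take two early terminators whose status at Day 29 later reaches the site, one dead and one alive. The first stays in the risk set until death and adds an event. The second leaves the risk set at last contact. How long each is followed is decided by how each fared. Kaplan-Meier, log-rank and Cox methods all require that censoring say nothing about later risk given what is already known, and here the derivation rule itself violates that.

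At stake are the mortality hazard ratio, its p-value and the plotted survival curves. If terminations, or the chance of learning of a later death, differ between arms, the bias does not cancel. The mortality sensitivity analyses in SAP 3.3.10, 6.4 and 9.4 deal with unblinding, crossover and concomitant therapy. None deals with this asymmetry.

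**Working it through.** **Inputs.** The rule and the 28-day horizon come from SAP 3.3.10. The documents give no figure for the effect of the rule, so there is none to reproduce. They also give no early-termination rate, no Day 29 mortality and no share of later deaths that would be learned. The planning scenarios in SAP section 5 put control-arm deaths at Day 15 at 1–3%. The following are therefore assumptions:
- Day 29 mortality: 10%, with 3% and 15% as alternatives.
- d, the share terminating early: 2%, 5% or 10%.
- q, the share of terminators' later deaths that is learned.
- h, terminators' hazard relative to the other subjects.

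**Step 1: a count by hand.** Take 1,000 subjects in an arm with 10% mortality. All terminations are at the start, h = 1 and q = 1. With no other censoring, the Kaplan-Meier mortality is deaths divided by those left in the risk set.
- d = 5%: 50 terminate, 5 die and are kept, 45 leave. 100/955 = 10.47%.
- d = 10%: 100 terminate, 10 die and are kept, 90 leave. 100/910 = 10.99%.

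**Step 2: the large-sample limit.** The formula is 1 − exp(−∫dN/Y), with exponential hazards, learned deaths kept at risk until death, and all other terminators leaving at termination. True mortality is 10%, h = 1, q = 1.

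| Timing of termination | d = 2% | d = 5% | d = 10% |
|---|---|---|---|
| Uniform over 28 days | 10.09% | 10.24% | 10.49% |
| All at Day 1 | 10.18% | 10.46% | 10.97% |

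The Day 1 row sits just below the hand count because termination is placed shortly after time zero. At 3% mortality, across the same values of d, the range is 3.03–3.16% (uniform) and up to 3.32% (Day 1). At 15% it is 15.13–15.70% and up to 16.37%.

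**Step 3: direction.** Let r be the risk of subjects who stay. Kaplan-Meier gives each terminator who leaves roughly the risk r of those remaining, and the learned deaths add q·h·r per terminator. Each terminator is thus credited with about r(1 + qh), against a true risk of about hr. The two agree when q = (h − 1)/h, which is 0.33, 0.50 and 0.67 for h = 1.5, 2 and 3. Above that value the curve is too high; below it, too low. With true mortality 10% and all terminations at Day 1:

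| d | h | q = 0.25 | q = 0.5 | q = 1 |
|---|---|---|---|---|
| 5% | 2 | 9.79% | 10.00% | 10.42% |
| 5% | 3 | 9.51% | 9.80% | 10.38% |
| 10% | 3 | 9.11% | 9.69% | 10.82% |

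**Step 4: between arms.** With no true effect, h = 1, q = 1 and 10% mortality, the apparent hazard ratio is about the ratio of cumulative hazards, ln(1 − KM) in one arm over the other.
- 2% v 10% terminating, uniform: ln(0.8951)/ln(0.8991) = 0.1108/0.1064 = 1.04.
- 2% v 10%, all at Day 1: ln(0.8903)/ln(0.8982) = 0.1162/0.1074 = 1.08.
- 2% v 5%, uniform: 0.1080/0.1064 = 1.015.

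**Step 5: against sampling error.** With 800 subjects and 10% mortality there are 80 deaths. The standard error of the log hazard ratio is about 2/√80 = 0.22. A ratio of 1.04 is 0.039/0.22, or 0.18 of a standard error; 1.08 is 0.077/0.22, or about 0.34. In simulations with no effect (400 per arm, 1,500 runs, uniform terminations), the log-rank test rejected 4–6% of the time, not distinguishable from 5%.

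**The case against.** The strongest reply is that little depends on this. The mortality percentage to be reported is the crude rate over all subjects in the arm, and early censoring does not shrink that denominator. The time-to-death table (SAP Table 61) shows a median, a hazard ratio and a p-value, so a Kaplan-Meier percentage would appear only as the height of a plotted curve. The bias in the hazard ratio is a fraction of a standard error. All of this stands and limits the importance of the point. It does not repair the hazard ratio or the curves, and the crude rate has its own weakness: it counts unknown status as alive.

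Second, the Day 15 analysis already carries forward subjects confirmed alive. That is partly right, but the sentence after it censors the same subject early if the last assessment came before Day 15. The two need reconciling.

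Third, a later report of survival could be read as a captured event. The SAP's only example is the end date of an adverse event, so the reading is possible but not secure.

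Two stronger readings are tempting, and the documents support neither. A reader might infer that mortality is certainly overstated. Step 3 shows that it can be understated, and incomplete learning of deaths is realistic: under Protocol 7.2, a subject who withdraws consent no longer permits efforts to obtain outcome data. A reader might also infer that unblinding drove differential termination. Enrollment was permitted until April 20, 2020 (SAP 4.1) and the unblinding procedure dates from April 29 (SAP 4.2.6). Unblinding is not termination, and subjects who stop study drug stay in the study unless they withdraw consent (Protocol 7.1.1). Unblinding and crossover also have their own mortality sensitivity analyses.

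**Conclusion.** The point holds as a defect in the stated rule, with modest consequences. Follow-up in the Day 29 time-to-death analysis depends on outcome, and no planned analysis addresses it.

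At an assumed 10% mortality, with 5–10% terminating, average-risk terminators and every later death learned, the curve is about 0.2 to 1.0 points too high. A spurious hazard ratio of 1.04–1.08 needs a marked imbalance, 2% v 10%. With higher-risk terminators and few deaths learned, the error is of similar size in the other direction. Neither sign nor size can be fixed from the documents, because they give no termination rate, no share of deaths learned and no evidence of an arm imbalance. That uncertainty is itself a reason to correct the rule, since a reader of the results could not tell which way the estimate leans.

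**What to change.** In SAP 3.3.10, apply post-termination vital status in both directions. A subject learned to have died before Day 29 is an event, and a subject learned to be alive is censored at the date last known alive, at most Day 29. This extends to Day 29 what the Day 15 text already does for subjects confirmed alive. Reword the two Day 15 sentences so that they agree, and say whether the rule also covers subjects lost to follow-up.

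Add a sensitivity analysis that censors every early terminator at last contact and ignores later deaths. Report early terminations and post-termination deaths by arm, so that readers can judge the possible bias.

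The cost is a few sentences and a small amount of extra derivation. There are two limits. The sensitivity analysis is itself biased low if terminators are at higher risk: with 5% terminating at twice the hazard and true mortality 10%, it gives about 9.6–9.8%. And symmetric censoring helps only where survival after termination is actually recorded; if deaths surface and survival does not, the asymmetry remains.

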3.3.11. Composite Endpoint of Death, SAEs, Severe AEs, Discontinuation of Study Infusions

A safety composite endpoint will be defined as the occurrence of at least one of the following through Day 29:

1. Death
2. SAE
3. Grade 3 or 4 AE

The time to this composite endpoint will be defined as the elapsed time (in days) from baseline to the earliest date of any of the events. Any subjects that are lost to follow-up or terminated early prior to experiencing any of the events will be censored at the day of their last observed assessment. Subjects who complete follow-up but do not experience any of the events will be censored at the day of their Day 29 visit.

4. INVESTIGATIONAL PLAN

4.1. Overall Study Design and Plan

This study is an adaptive, randomized, double-blind, placebo-controlled trial to evaluate the safety and efficacy of novel therapeutic agents in hospitalized adults diagnosed with COVID-19. The study is a multicenter trial that will be conducted in up to approximately 100 sites globally. The study will compare different investigational therapeutic agents to a control arm. There will be interim monitoring to allow early stopping for futility, efficacy, or safety. If one therapy proves to be efficacious, then this treatment may become the control arm for comparison(s) with new experimental treatment(s). Any such change would be accompanied by an updated sample size. Because background standards of supportive care may evolve/improve over time as more is learned about successful management of COVID-19, comparisons of safety and efficacy will be based on data from concurrently randomized subjects. An independent Data and Safety Monitoring Board (DSMB) will actively monitor interim data to make recommendations about early study closure or changes to study arms.

Recruitment will continue until there are 400 subjects with a “recovered” status (per the primary objective). The primary analysis will be based the total number of subjects enrolled to achieve 400 recoveries. An additional analysis of the moderate severity subgroup (those with baseline status of “Hospitalized, requiring supplemental oxygen” or “Hospitalized, not requiring supplemental oxygen - requiring ongoing medical care”) is also of public health importance. Hence, enrollment will be permitted until the date of April 20, 2020 to ensure 400 recoveries and provide additional data about this important subgroup. With recent enrollment rates, the total sample size may be 600 to over 800.

If any additional therapeutic arms are added, the sample size will be recalculated.

Subjects will be assessed daily while hospitalized. If the subjects are discharged from the hospital, they will have a study visit at Days 15, 22, and 29. For discharged subjects, it is preferred that the Day 15 and 29 visits are in person to obtain safety laboratory tests and OP swab and blood (serum only) samples for secondary research as well as clinical outcome data. However, infection control or other restrictions may limit the ability of the subject to return to the clinic. In this case, these visits may be conducted by phone, and only clinical data will be obtained. The Day 22 visit does not have laboratory tests or collection of samples and may also be conducted by phone.

The primary outcome is time to recovery by Day 29. The primary analysis will include data from both severity groups using a stratified log-rank test. A key secondary outcome evaluates treatment-related improvements in the 8-point ordinal scale at Day 15. As little is known about the clinical course of COVID-19, an evaluation of the pooled (i.e., blinded to treatment assignment) proportion recovered will be used to gauge whether the targeted total number of subjects in the recovered categories of the ordinal scale will be achieved with the planned sample size. The analysis of the pilot data will be blinded, allowing for the pilot data to be included in subsequent analyses.

The study will randomize subjects 1:1 to placebo or investigational product. In absence of an established treatment, the use of placebo is justified. If additional arms are added to or dropped from the trial, randomization will proceed with an equal probability of assignment to each of the

remaining arms. Randomization will be stratified by site and severity (severe versus mild-moderate). See Section 4.2.3 for more information on randomization and stratification.

4.2. Selection of Study Population

Male and non-pregnant female adults ≥ 18 years of age or older with COVID-19 and who meet all eligibility criteria will be enrolled at up to approximately 100 clinical trial sites globally. The target population should reflect the community at large.

Inclusion Criteria

In order to be eligible to participate in this study, a patient must meet all of the following criteria:

1. Admitted to a hospital with symptoms suggestive of COVID-19 infection.
2. Subject (or legally authorized representative) provides informed consent prior to initiation of any study procedures.
3. Subject (or legally authorized representative) understands and agrees to comply with planned study procedures.
4. Male or non-pregnant female adult ≥ 18 years of age at time of enrollment.
5. Has laboratory-confirmed SARS-CoV-2 infection as determined by PCR or other commercial or public health assay in any specimen, as documented by either of the following:
 - PCR positive in sample collected < 72 hours prior to randomization; OR
 - PCR positive in sample collected ≥ 72 hours prior to randomization, documented inability to obtain a repeat sample (e.g. due to lack of testing supplies, limited testing capacity, results taking > 24 hours, etc.). AND progressive disease suggestive of ongoing SARS-CoV-2 infection.
6. Illness of any duration, and at least one of the following:
 - Radiographic infiltrates by imaging (chest x-ray, CT scan, etc.), OR
 - $SpO_2 \leq 94\%$ on room air, OR
 - Requiring supplemental oxygen, OR
 - Requiring mechanical ventilation.
7. Women of childbearing potential must agree to either abstinence or use at least one primary form of contraception not including hormonal contraception from the time of screening through Day 29.
8. Agrees to not participate in another clinical trial for the treatment of COVID-19 or SARS-CoV-2 through Day 29.

Exclusion Criteria

An individual who meets any of the following criteria will be excluded from participation in this study:

1. ALT/AST > 5 times the upper limit of normal.

2. Estimated glomerular filtration rate (eGFR) < 30 ml/min (including patients receiving hemodialysis or hemofiltration).
3. Pregnancy or breast feeding.
4. Anticipated discharge from the hospital or transfer to another hospital which is not a study site within 72 hours.
5. Allergy to any study medication.

4.2.1. Treatments Administered

Subjects will receive either remdesivir through an IV in a loading (200 mg) dose followed by up to 9 maintenance (100 mg) doses or placebo at an equal volume at the same schedule.

4.2.2. Identity of Investigational Product(s)

Remdesivir is a single diastereomer monophosphoramidate prodrug designed for the intracellular delivery of a modified adenine nucleoside analog GS-441524. In addition to the active ingredient, the lyophilized formulation of remdesivir contains the following inactive ingredients: water for injection, sulfobutylether β -cyclodextrin sodium (SBECD), and hydrochloric acid and/or sodium hydroxide.

The supplied matching placebo lyophilized formulation is identical in physical appearance to the active lyophilized formulation and contains the same inactive ingredients. Due to limitations on placebo supplies, normal saline may be given at an equal volume as a placebo in place of the lyophilized formulation.

4.2.3. Method of Assigning Subjects to Treatment Groups (Randomization)

Enrollment and randomization of subjects is done online using the enrollment module of Advantage eClinical[®].

Eligible subjects will be randomized and assigned in a 1:1 ratio to either remdesivir or placebo, with stratification by site and disease severity (Mild/Moderate disease or Severe disease). The randomization is based on a variable blocked scheme to provide an approximately balanced allocation to the treatment groups during the study. If arms are added or removed later in the study, randomization will continue in an equal allocation manner.

4.2.4. Selection of Doses in the Study

The dose of remdesivir used in this study will be the same dose that has been used in the human Ebola clinical trials.

4.2.5. Selection and Timing of Dose for Each Subject

Each subject is randomly assigned to a treatment group as described in Section 4.2.3. Study product is given on Day 1 as a loading dose and daily up to 9 days after as maintenance doses. The dose should be given the same time each day (+/- 2 hours).

4.2.6. Blinding

The treatment will be prepared by the licensed pharmacist and administered by blinded study personnel or hospital staff. All follow-up safety and efficacy evaluations will be performed by blinded clinic staff.

The unblinded pharmacist at each site will refer to the Treatment Key provided for the trial by the SDCC to determine the treatment for the subjects. The pharmacist will maintain an open label code (provided by the SDCC) under locked/secured conditions and will follow the randomization code. Due to limitation on placebo supplies, normal saline may be given at an equal volume as a placebo in place of the lyophilized formulation. In this case, IV bags of study treatment (both Remdesivir and placebo) will be covered to mask the slight color difference between the Remdesivir solution and placebo to maintain the study blind.

After the public disclosure of the interim results, an unblinding procedure was added (per April 29, 2020 Protocol Administrative Letter) in which an investigator could unblind a subject and potentially initiate remdesivir treatment if one of the following criteria is met:

1. Potential remdesivir treatment, only for subjects meeting all of the following criteria:
 - a. On study (i.e. have not completed the Day 29 visit)
 - b. Hospitalized
 - c. It is clinically indicated (i.e., those that are doing poorly)
2. Subject/LAR request, only for subjects meeting one of the following criteria:
 - a. Subject is no longer hospitalized and has completed the study (on or after Day 29 visit), or
 - b. After death.

